Specific Aim 1: To investigate that increased DA transmission normalizes reward responsiveness and optimism in females with histories of CSA. We will use reward paradigms from our pilot work in conjunction with a pharmacological challenge to test that decreased phasic DA transmission within mesolimbic regions plays a key role in CSA sequelae. We hypothesize that increased phasic DA release – achieved through presynaptic DA autoreceptor blocking by means of single low dose of the D₂/D₃ antagonist amisulpride – will improve positive reinforcement learning and boost activation in reward-related brain regions, particularly the ventral and dorsal striatum (**Hypothesis 1a**). Due to hypothesized downregulation of mesolimbic DA pathways, we expect that individuals with CSA and current MDD (“CSA/MDD”) will show the largest improvements. Confirming that a well-functioning reward system is a marker of resilience, adults with CSA without lifetime psychopathology (“CSA/RES”) will show normative activation and performance under placebo (**Hypothesis 1b**). We also hypothesize that increased phasic DA release – achieved through amisulpride – will re-orient MDD individuals from a pessimistic outlook to an optimistic outlook as measured by the Optimism Bias Task (**Hypothesis 1c**). In addition, under placebo, MDD participants will show a pessimistic outlook as compared with healthy controls (**Hypothesis 1d**).

Specific Aim 2: To investigate dopamine transporter and its relation to reward processing in females with CSA history. We will utilize positron emission tomography (PET) and a highly selective radioactive ligand (¹¹C-altropane) to assess DAT binding in CSA adults. Animal studies have shown that early adversity leads to DAT downregulation within mesolimbic regions. In humans, we have observed links between altropane binding and depressive symptoms, the most common CSA sequelae). Based on our data, we expect that, relative to control and CSA/RES subjects, CSA/MDD adults will show reduced altropane binding (**Hypothesis 2a**). We further hypothesize that, among the CSA/MDD group, reduced DAT will correlate with blunted reinforcement learning and striatal activation (**Hypothesis 2b**).

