Images will be acquired in 3-D mode and reconstructed using a filtered back projection method while modeling the point spread function of the HR+ in the projector to ensure recovery of in-plane spatial resolution of ~ 4.5 mm without increasing noise levels. All projection data will be corrected for nonuniformity of detector response, dead time, random coincidences, and scattered radiation. After realignment, motion-corrected PET frames will be summed, registered to the respective MRI (Woods et al 1993), and transformed into stereotaxic space (Talairach & Tournoux 1988) based on an automated feature-matching algorithm (Collins et al 1994). ROIs will be manually drawn on high-resolution MRI images for dorsal (caudate, putamen) and ventral (NAc) striatal regions. The cerebellum will be used as reference tissue. A simplified reference tissue method (Gunn et al 2001; Lammertsma & Hume 1996) will be used to calculate binding potential. To increase statistical power, a Bayesian method recently developed by the MGH team will be used (Alpert et al 2009; Fang et al 2010). Briefly, this method utilizes prior normative data in a cohort of 51 healthy subjects who underwent 60-min ^{11}C -altropane scan. Bayesian estimates yielded a substantial variance reduction in SRTM parameters, making it possible to reduce the sample size needed to achieve a given power level by $\sqrt{2}$. ANOVAs contrasting age-adjusted altropane binding (covariates: smoking & phase of menstrual cycle) across the groups will be performed. Correlational analyses between binding and (1) response bias in the probabilistic reward task, and (2) beta weights in striatal regions during the reward task, will be run.

Skin Fibroblast Analyses

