a single dose of pramipexole – hypothesized to reduce phasic DA transmission due to inhibition of presynaptic autoreceptors – had significantly lower reward learning than those receiving placebo ($d = -1.45$; [name] et al 2008b). In an fMRI study using the MID task, relative to controls, a maltreated sample showed weaker activation to reward-predicting cues in the left putamen ($d = -0.54$) and left pallidus ($d = -1.02$), yielding a mean effect size of -0.78 . In a separate study using the MID task, unmedicated MDD subjects showed weaker activation than controls in response to gains in the caudate ($d = -0.98$), left NAc ($d = -0.73$) and left putamen ($d = -0.78$) during reward anticipation ([name] et al 2009a), yielding a mean effect size of -0.87 . In a pharmacological fMRI study in unmedicated MDD subjects we found that a single 150 mg dose of Bupropion – assumed to partially block DAT – increased reward-related responses in components of the brain’s reward circuit, including the midbrain ($d = -1.88$), subcallosal gyrus ($d = -1.64$), and SLEA ($d = -1.89$), leading to an mean effect size of -1.80 ([name] et al 2008a). In sum, based on the effect sizes we have observed for the behavioral (mean $d = -1.00$) and fMRI (mean $d = -1.15$) components, a total of 92 subjects leads to a power >0.95 of detecting group differences.

For the PET study, secondary analyses of altropane data collected in ADHD and control samples (Spencer et al 2007) indicated that a history of depression and/or current subthreshold depressive symptoms were linked to decreased DAT binding ($d = -0.58$). Because this sample was carefully screened to exclude current, clinically significant depressive symptoms and because analyses did not involve the recently developed Bayesian method, we expect that effect size between control and CSA/MDD groups will be larger (expected $d > 0.80$). Thus, 92 subjects leads to a power >0.85 of detecting group differences.

VII. RISKS AND DISCOMFORTS

a. Complications of surgical and non-surgical procedures

Maastricht Acute Stress Test (MAST)

The risks associated with the stress manipulation are minimal. This manipulation has been implemented in numerous labs due to its efficiency and safety. First of all, it is a non-intrusive manipulation that causes only very minor pain, if any. Secondly, at all times participants are allowed to remove their hand from the cold water and thus immediately stop the manipulation.

EEG

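### The PET binding estimator borrows from a healthy-cohort prior; the plan counts only its variance gain, carries that gain into the planned effect size, and has no prior-free check

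*Combined protocol and SAP*

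**What the plan says.** All references are to the combined protocol and SAP.

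- **Estimator (Section VI.a, PET Analyses).** A simplified reference tissue method (SRTM) "will be used to calculate binding potential". The plan then adds: "To increase statistical power, a Bayesian method recently developed by the MGH team will be used". Of this method it says "this method utilizes prior normative data in a cohort of 51 healthy subjects".
- **Benefit claimed (same section).** "Bayesian estimates yielded a substantial variance reduction in SRTM parameters". The plan converts this into a saving in sample size, at fixed power, of √2.
- **Analysis (same section).** "ANOVAs contrasting age-adjusted altropane binding (covariates: smoking & phase of menstrual cycle) across the groups will be performed". Binding is also correlated with response bias and with striatal beta weights.
- **Hypothesis 2a (Section II.a, Specific Aim 2).** The prediction is that "relative to control and CSA/RES subjects, CSA/MDD adults will show reduced altropane binding".
- **Power (Section VI.d).** Earlier altropane data gave d = -0.58. Two reasons are offered for planning on d > 0.80. The first is that the earlier sample had been screened to exclude current, clinically significant depressive symptoms. The second is "because analyses did not involve the recently developed Bayesian method, we expect that effect size between control and CSA/MDD groups will be larger". The section concludes that 92 subjects give power above 0.85.

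The plan does not say which SRTM parameters carry the prior, where it is centred, how heavily it is weighted, or whether it is used in every group. No analysis of prior-free binding is listed.

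**The concern.** A prior built on healthy subjects suits the controls. It may be off-centre for any group whose binding truly differs, and a difference of that kind is what Hypothesis 2a sets out to measure. If the prior carries weight on binding potential, it reduces the between-subject spread and the between-group difference together. The plan counts the first effect and is silent on the second.

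Two things are at stake. The first is the size of the DAT deficit in binding units, which could be understated with nothing in the report to show it. The second is the power case: the variance gain enters the planned d as if the group difference were left intact. Appendix 2 makes the first point concrete. It reports interim PET findings of lower DAT binding in MDD than in controls, although it does not say which estimator produced them.

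**Working it through.** **Inputs from the documents.** 23 per group, alpha 0.05 (sidedness not stated), earlier d = 0.58 without the Bayesian method, planned d = 0.80, stated power above 0.85, sample-size saving √2 (read as n divided by √2).

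**Input assumed.** w is the weight on the subject's own data, taken from 0.90 to 0.50, with the prior centred on the control mean. The documents give no weight.

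**1. The plan's own figure.** Two-group comparison, n = 23 per group, d = 0.80:
- one-sided: 0.857 (normal), 0.848 (t test)
- two-sided: 0.774 (normal), 0.756 (t test)

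The stated figure is therefore reproduced at d = 0.80 with a one-sided normal calculation, but not with a two-sided two-group test.

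**2. The Bayesian gain at face value.** Dividing n by √2 at fixed power means variance × 1/√2, so SD × 2^(-1/4) = 0.841. If the group difference is untouched, d = 0.58 × 2^(1/4) = 0.69. Two-sided t-test power at 23 per group:
- d = 0.58: 0.49
- d = 0.69: 0.63
- d = 0.80: 0.756

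Even in full, the gain does not reach 0.80. The rest (0.80/0.69 = 1.16) must come from the other reason. Without the gain, that reason must supply all of 0.80/0.58 = 1.38.

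**3. The same gain as uniform shrinkage of binding.** Estimate = w·x + (1 - w)·m, where x is the prior-free value and m the prior centre. The centre cancels from any group contrast, so difference × w, SD × w, d unchanged.

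| w | Loss of raw difference | d |
|---|---|---|
| 0.90 | 10% | 0.58 |
| 0.841 (whole √2 saving) | 16% | 0.58 |
| 0.707 | 29% | 0.58 |
| 0.50 | 50% | 0.58 |

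A simulation of 20,000 trials at w = 0.841 agrees: the difference went from 0.583 to 0.490, the SD from 0.999 to 0.840, d stayed at 0.583, and two-sided power was 0.489 before and after.

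**4. Weights that differ by group (assumed 0.9 and 0.7).** With raw SD 1 in both groups, the pooled SD after shrinkage is √((0.81 + 0.49)/2) = 0.806.
- Patients noisier (0.9 controls, 0.7 patients): d = 0.7 × 0.58/0.806 = 0.50, power 0.39.
- Controls noisier (0.7 controls, 0.9 patients): d = 0.9 × 0.58/0.806 = 0.65, power 0.57.

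If the raw SD is instead allowed to be larger in the noisier group, the results are 0.51 with power 0.40, and 0.66 with power 0.59.

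**The case against.** The strongest reply is that the mechanism is inferred. The section is a short summary of a published method. The prior may act mainly on other kinetic parameters and steady the fit without pulling binding far toward healthy values. The √2 claim would then be largely real and the attenuation small. This stands, and it is why every attenuation figure above is conditional. The plan does not say so, however, and a prior-free run would show it.

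Some gain is also possible when the prior does act on binding. If scan noise varies strongly between subjects but not by group, simulated d rises from 0.58 to 0.59 at w = 0.841 and to 0.63 at w = 0.50. That is real, but smaller than the gain credited.

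Three stronger readings are tempting, and the documents do not support them:
- **That the prior could manufacture the predicted result.** Equal-weight shrinkage works against the CSA/MDD-control difference, so it is conservative for Hypothesis 2a.
- **That similarity of CSA/RES to controls is built into a PET conclusion.** Hypothesis 2a predicts only that CSA/MDD is lower than both. Similarity of CSA/RES to controls is predicted for reward activation and performance, reward sensitivity and cortisol, and the fibroblast phenotype, not for binding.
- **That the Hypothesis 2b correlations are necessarily distorted.** A common weight leaves correlations unchanged.

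**Conclusion.** The point holds in a limited form. The text establishes that the prior comes from healthy subjects, that only its variance benefit is counted, that this benefit supports the planned d, and that no prior-free analysis is listed. Use in all four groups is the plain reading, because one estimator feeds one ANOVA, but it is not stated.

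The consequence depends on how far the prior informs binding potential. If the whole √2 saving is uniform shrinkage, the raw DAT difference is understated by about 16% and the saving buys no power. The 10% to 50% range is assumed. If weights differ by group, d could move from 0.58 to about 0.50 or 0.65 under the assumed weights, depending on whose scans are noisier.

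The part that needs no assumption about the prior is the power arithmetic: the stated saving alone takes d to 0.69, not 0.80. A reader should not go further and infer that the PET tests are invalid; with equal weights they give the same p-values with or without the prior.

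**What to change.** 1. **Section VI.a.** Add the conventional SRTM binding potential, without the healthy prior, as a sensitivity analysis for Hypotheses 2a and 2b in all groups. Report it beside the Bayesian result, with raw group differences from both. State which parameters carry the prior, its centre and weight, and the groups in which it is used.
2. **Section VI.d.** Do not count the Bayesian variance gain toward d > 0.80 unless the group difference is shown to survive it. State whether the test is one- or two-sided.

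I would not make a group claim depend on agreement between the two estimators, since that adds a second hurdle with only 23 per group. Nor would I substitute a prior pooled over the four study groups: with equal weights the centre cancels, so it cuts the raw difference by the same factor, and it uses the study data twice.

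**Cost.** One further run, on the same scans, of a model the plan already names. The prior-free estimates will be noisier, and a disagreement may need explaining. The check would also be added after the interim PET results in Appendix 2 were seen, and the report should say so.

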Procedure: Because the pharmacokinetics of amisulpride are linear and similar across gender, and a first peak plasma concentration is seen 1-1.5 hr after oral administration (Ascalone et al, 1996), fMRI scanning will start 1 hr after administration of amisulpride (or placebo). During the one-hour wait between the administration of amisulpride (or placebo), participants may read or view a neutral film. During this time, experimenters will carefully monitor participants to assess the presence/absence of side effects. A designated study physician will be present at the neuroimaging facility throughout the session with a response time of 2-3 minutes in case study participants experience adverse side effects during the fMRI scanning. After one hour, participants will be asked to enter the scanner, and data collection will begin. The dose (50 mg) was selected based on prior studies (Hamon-Vilcot et al., 1998; Samuels et al, 2006), and the observation that all prior studies using amisulpride in depressive disorders have used 50 mg/day doses (see above). Using a double-blind design, half of the participants in each group will be administered amisulpride, whereas the other half will receive placebo.

c. Devices to be used

Not applicable

d. Surgical interventions

Not applicable

e. Data to be collected

Please see below for details on data collected and analyses performed.

VI. BIostatistical Analysis

a. Specific data variables being collected

Probabilistic Reward Task (PRT)

The main variable is response bias, which assesses participants' preference for the stimulus paired with more frequent reward, and will be calculated using a published formula ([name] et al 2005). To test the specificity of findings, control analyses will be run on discriminability, which provides a measure of the ability to discriminate the two stimuli. To test **Hypothesis 3a** and **3b**, *Group* (CSA/MDD, CSA/RES, MDD, controls) x *Block* (1,2,3) ANOVAs will be run for response bias and discriminability.

Implicit Learning Serial Reaction Time Task (SRTT)

SRTT data will be analyzed using established procedures (median reaction times for blocks presenting random vs. the predetermined sequence will be calculated; (Kathmann et al, 2005). If group differences emerge in procedural learning, SRTT data will be used as covariates/regressors in all analyses.

Optimism Bias Task

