For each trial we compare the extent to which participants altered their estimates in response to the information presented (update score = second estimate- first estimate). We then compare these scores for trials in which participants receive good news (trials where the actuarial probability of a negative event is less than participants' estimate of their likelihood) with trials in which they receive bad news trials (where the actuarial probability of a negative event is greater than participants estimate of their likelihood).

Self-Concept Attention Task

Reaction time (RT) and responses to trait words are compared between the accompanying image types (self, other person, or scrambled).

Scalp ERP and Source Analyses

ERP analyses will follow prior work ([name] et al 2002, 2003). ERPs will be collected during the Probabilistic Reward Task. Briefly, ERPs will be computed covering 1024 ms and time-locked to the onset of the stimulus (Rich, Lean) and feedback using a 100-ms pre-stimulus baseline. Analyses will focus on the feedback-related negativity (FRN). The FRN (measured as the most negative deflection 200-400ms after reward feedback over fronto-central electrodes) is hypothesized to reflect phasic DA reward prediction signals projecting from the basal ganglia to the ACC and used to guide behavior according to reinforcements (Holroyd & Coles 2002). Studies in the PI's lab have shown that reduced reinforcement learning is linked to a larger (i.e., more negative) FRN, likely due to a reliance on external feedback to guide behavior (Bogdan et al 2011; Santesso et al 2008, 2009). Thus, relative to controls, the CSA/MDD – but not CSA/RES group – will show larger FRN and reduced OFC and vmPFC activation to reward feedback. *Group x Electrode* (AFz, Fz, FCz, Cz) ANOVAs will be conducted on FRN amplitude and latency. As in prior work (Bogdan et al 2011; Santesso et al 2008), intracortical current density will be computed at the time of the FRN using LORETA (Pascual-Marqui et al 1999). Whole-brain voxelwise tests will test differences between groups or conditions. To control for Type I error, permutation procedures will be used to calculate the false-positive rate under the Null Hypothesis (Nichols & Holmes 2002).

Amisulpride Behavioral Analyses for PSST and MID

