Comparison of Molecular and Cellular Properties of Converted DA Neurons from Fibroblasts of MDD/CSA (n=8), CSA/RES (n=4), and Psychiatrically Healthy Subjects (n=8): Once we optimize conversion of fibroblasts to mDA neurons, we will use these biopsied fibroblasts to convert them to mDA neurons using our optimized protocol. To evaluate whether converted DA neurons from each group have distinct properties, we will test their ability to synthesize and release DA in response to membrane depolarization. We will treat *in vitro* differentiated cells with 50 mM KCl for 30 minutes and assess DA release by HPLC. Media will be collected after 30 min then concentrated perchloric acid (PCA) will be added to a final concentration of 0.1 M PCA/0.1mM EDTA. The DA content of the supernatants will be measured by reverse-phase HPLC. We will also compare mRNA expression patterns for dopamine-related genes such as synthesizing (TH and AADC), uptake (DAT), degrading (MAO and COMT), and storage function (VMAT2) at mRNA and protein levels in converted mDA neurons of each group.

Plasma Samples

Concentrations of pro- and anti-inflammatory cytokines and related receptors will be assessed using enzyme-linked immunosorbent assays (ELISA, R&D systems, Minneapolis, MN). All assays will be performed at the CLIA-certified Harvard Catalyst Central Laboratory (HCCL) in accordance with manufacturer specifications, and will be run in duplicate.

b. Study endpoints

Not applicable

c. Statistical methods

Please see above.

d. Power analysis

Sample size and power calculations

Sample size was estimated after considering effect sizes obtained in preliminary studies. Effect sizes were calculated using $p = 0.05$ for detecting differences between (1) controls vs. CSA/MDD, and (2) CSA/MDD receiving a DA challenge vs. placebo. Based on these estimates and allowing for 5% data loss, the sample size is 92 (23 subjects/group). In our study using the PSST task proposed, relative to controls, women with histories of CSA and MDD showed lower accuracy in trials in which they needed to rely on reward (Cohen's $d = -0.85$). In a study using the probabilistic reward task, we found that unmedicated MDD subjects had significantly reduced response bias compared to controls ($d = -0.70$; [name] et al 2009b). In another study using the same task, we found that healthy subjects receiving

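### H2a and H3a say CSA/MDD differs in a stated direction from two named groups, but the PET, PRT and FRN analyses only test for any difference among the groups

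*Combined protocol and SAP*

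**What the plan says.** Section II.a, Specific Aim 2, states H2a: "relative to control and CSA/RES subjects, CSA/MDD adults will show reduced altropane binding". Specific Aim 3 states H3a against the same two comparators: after acute stress, CSA/MDD will show lower vmPFC activation, higher cortisol reactivity and poorer reward learning.

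The group tests are in section VI.a:

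- **PET Analyses:** "ANOVAs contrasting age-adjusted altropane binding (covariates: smoking & phase of menstrual cycle) across the groups will be performed". The groups are not listed and no hypothesis number is cited, but this is the only group test of binding.
- **Probabilistic Reward Task:** for H3a and H3b, Group (four levels) x Block "ANOVAs will be run for response bias and discriminability".
- **Scalp ERP and Source Analyses:** the text expects a larger FRN in CSA/MDD, but not in CSA/RES, relative to controls. Group x Electrode "ANOVAs will be conducted on FRN amplitude and latency".

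No contrast, post-hoc procedure or direction rule is attached to these three. The PSST/MID and fMRI sections do name planned contrasts. Section VI.c only refers back to this text. Section VI.d bases its effect sizes on controls v CSA/MDD and on drug v placebo within CSA/MDD, and concludes that "the sample size is 92 (23 subjects/group").

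**The concern.** A four-group F test has three degrees of freedom and no direction. It rejects when any group departs from the others. H2a and H3a are narrower: one group, two comparators, one direction. The plan does not say how a significant F becomes a statement about CSA/MDD, so the deciding comparison would be chosen after the F is seen.

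This matters because the study exists to separate effects of abuse from effects of depression. Appendix 2 already reports interim PET results showing lower DAT binding in MDD than in controls, without separating CSA/MDD from MDD. The Randomization section says the drug blind has been broken for preliminary analyses. A comparison picked at this stage is open to challenge, whereas one read directly off the hypotheses in section II is not.

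**Working it through.** **Inputs.** From section VI.d: 92 subjects, 23 per group; p = 0.05; expected PET d above 0.80 for controls v CSA/MDD; PRT d = 0.70; observed DAT d = 0.58; behavioural mean d = 1.00. Assumptions: two-sided tests (sidedness is not stated), equal SDs, one score per subject, and the position of the MDD group varied.

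**The plan's own figure.** PET power is given as above 0.85. For 23 v 23 at d = 0.80, a two-sided t test gives 0.756. A one-sided test gives 0.848 (t) or 0.857 (normal approximation). Two other variants also clear 0.85: an omnibus F with f = d/2 = 0.40 (0.898), and a two-sided t test with n multiplied by √2 for the Bayesian PET method (0.888). The plan does not say which was used.

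**Formulas.** Write μ for the group means in SD units and n = 23.

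- Omnibus: λ = n Σ(μᵢ − μ̄)², noncentral F(3, 88).
- Pairwise contrast: δ = 0.8/√(2/23) = 2.71, noncentral t(88), power 0.765.
- Pooled contrast, CSA/MDD v the mean of controls and CSA/RES: δ = 0.8/√(1.5/23) = 3.13, power 0.873.
- Both pairwise contrasts: simulated, since they share the CSA/MDD mean.

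**Worked cases.**

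- Only MDD 0.8 lower: μ̄ = −0.2, Σ = 3(0.2²) + 0.6² = 0.48, λ = 23 × 0.48 = 11.04, P = 0.786.
- CSA/MDD 0.8 higher: same λ, same P.
- CSA/RES and CSA/MDD both 0.8 lower, MDD at the control level: Σ = 4(0.4²) = 0.64, λ = 14.72, P = 0.898. The pooled contrast is then 0.4, δ = 0.4/√(1.5/23) = 1.57, P = 0.341.

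Probability of a significant result (last column: both contrasts significant in the predicted direction):

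| True pattern (0.8 SD shifts) | H2a | Omnibus F | Pooled contrast | Both contrasts |
|---|---|---|---|---|
| Only CSA/MDD lower | true | 0.786 | 0.873 | 0.64 |
| CSA/MDD lower, MDD halfway | true | 0.746 | 0.873 | 0.64 |
| CSA/MDD and MDD equally lower | true | 0.898 | 0.873 | 0.64 |
| Only MDD lower | false | 0.786 | 0.05 | at most 0.025 |
| CSA/MDD higher | false | 0.786 | 0.873, wrong sign | near 0 |
| CSA/RES and CSA/MDD equally lower | false | 0.898 | 0.341 | 0.025 |

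The 0.025 entries follow because at least one required contrast is truly null there, and a two-sided 0.05 test rejects in the predicted direction 2.5% of the time.

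**Sensitivity.** If only MDD is lower, the omnibus is significant with probability 0.484 at d = 0.58, 0.659 at 0.70 and 0.941 at 1.00. Power for both contrasts is about 0.50 at d = 0.70 and 0.86 at 1.00. With 22 per group (5% loss) at d = 0.80, the omnibus figure is 0.764 and each pairwise contrast has 0.746.

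**The case against.** **The ANOVAs may be shorthand.** The authors state their expected patterns, and the ERP section names a direction and comparators. A sensible analyst would follow a significant F with the obvious comparisons. That is fair as to intent, but the same section VI.a writes planned contrasts out for PSST/MID and fMRI, and nothing extends them to PET, PRT or FRN.

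**Only the PRT ANOVA is tied by number to H3a and H3b.** This stands. The PET link to H2a is inferred. The FRN is not one of H3a's outcomes; its ANOVA bears on the ERP section's own prediction. The vmPFC part of H3a is addressed by voxelwise source tests with permutation control.

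**The omnibus is not clearly weaker.** This also stands. A reader might infer a general power loss of roughly 9 to 13 points across all three measures. That range arises only for PET at d = 0.80, against a pooled comparator, with MDD at the control level or halfway. At d = 0.80 the comparison runs from a 2.5-point gain for the omnibus to a 14-point loss, depending on where MDD lies. Against the pairwise comparison in section VI.d, the omnibus has 0.746 to 0.786 v 0.765 in those two cases, which is no material difference. No FRN effect size is given, and the repeated-measures PRT and FRN tests cannot be powered without a within-subject correlation.

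**Requiring both contrasts costs power.** It does: 0.64 v 0.87 for the pooled contrast. But the pooled contrast fails on the alternative H2a most needs to exclude, that resilience makes no difference among abused women. It is then significant 34% of the time at d = 0.80 and 49% at d = 1.00.

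**Conclusion.** The point holds as one of validity. The omnibus F does not test H2a or H3a. Under the PET assumption it would be significant 79% of the time in situations where H2a is false, including one where the effect has the wrong sign. The figures assume 23 per group, equal SDs, a two-sided 0.05 level, shifts of 0.8 SD and a single score per subject. For PRT and FRN they illustrate the logic and are not power estimates.

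Two further inferences are not supported. H3b should not be treated as another single directional contrast. Its reward and cortisol parts predict similarity between CSA/RES and controls, which a difference test cannot support. On its directional vmPFC part the omnibus is not weaker (0.786 v 0.765 at a shift of 0.80). Nor can a power figure be attached to the prediction that CSA/MDD gains most from amisulpride: the stated test is a three-way interaction with a within-subject factor, and the plan gives neither the drug effects by group nor the correlation needed.

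**What to change.** In the PRT, ERP and PET parts of section VI.a, add two contrasts estimated from the four-group model with pooled error: CSA/MDD v controls and CSA/MDD v CSA/RES. For each outcome:

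- State the predicted direction and whether the test is one- or two-sided.
- Do not make the contrasts conditional on the omnibus F. Keep the F as descriptive.
- Declare H2a, the reward-learning part of H3a, or the FRN prediction supported only if both contrasts are significant in the predicted direction. Because both are required, each can be tested at 0.05 without adjustment. The FRN text names CSA/RES only as not differing from controls, so the authors should confirm that the second contrast is what they intend there.
- A pooled contrast may be reported alongside but should not stand alone.

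Add to section VI.d that, at d = 0.80, power is about 0.64 for both contrasts (two-sided) and 0.765 for each alone. Handle H3b's similarity claims separately, with an equivalence margin.

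The change takes a few sentences and needs no new data. The real cost is a joint power below the stated 0.85. The contrasts come from hypotheses already in section II, so they can still be fixed without reference to the interim results, and this should be done before the final analysis.
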